7.2 Aim 2 Measures and Analyses

Based on our existing data for PLWH SMS compliance, we anticipate that participants will respond to 80-90% of the daily text messages during IMPACT. To address the issue of missing data, we will incorporate questions that allow participants to indicate their pain and cannabis use for the prior day if they did not respond to the earlier message. For days that have completely missing data, we will treat the intermittently missing data as missing completely at random. However, this assumption will be checked in sensitivity analyses by comparing the outcomes of participants based on the amount of missing data. Study dropout will be examined separately using statistical methods in current use [Diggle, Heagerty, Liang, and Zeger, *Analysis of Longitudinal Data*, 2nd ed., Oxford University Press, 2013]: The relationship between CBD, THC, and the CBD/THC ratio during a cannabis exposure event to changes in pain before and after the event will be examined using longitudinal data methods – e.g., mixed-effects linear models, controlling for potential confounders including baseline pain, in addition to those listed under Aim 1. The total CBD and THC consumed during the exposure will be calculated using the SUI method, estimating total grams of cannabis consumed multiplied by the percentages of CBD and THC content. Subject-specific random intercepts will be included in the model in order to account for the within-subject correlation of the outcome. Exploratory analyses will examine if there are different effects of reported cannabis strain (Sativa, Indica), individual types (e.g., OG Kush, Sour Lemon, etc.), or mode (smoking, vaporizing, ingesting food product) on pre-post changes in NP. We will also conduct exploratory analyses to examine if there is an interaction between reported levels of THC (low, < 1%, medium, 1-6%, high, > 10%) and CBD (low, < 1%, medium, 1-6%, high, > 10%) on pain change after drug use. The association of daily measures of pain levels with HRV will use a linear mixed-effects model, adjusting for potential confounders. The within-subject correlation will be accounted for using subject-specific random intercepts. Longitudinal changes in HRV between the first and last week will be assessed with a linear model that includes cannabis use (light vs. heavy) and CBD/THC intake, as predictors. Regression analyses will also examine the association between HRV and self-report pain measures quantified at the baseline and final visits.

Comparison of NIDA-obtained and dispensary-obtained cannabis effects on NP. We will compare the effect of laboratory cannabis administration and IMPACT self-report data on changes in pain (both measured with NPRS) before and after drug exposure. We will assess pain change scores for the laboratory study and IMPACT measured as the difference between

baseline (before drug) and 60 and 120 minutes after drug, time points that correspond with pain reduction in our prior THC work⁶⁰. We will use the following analyses: 1) plot the distribution of the CBD/THC ratio (x-axis) against pain change (y-axis), calculate the slope of pain change scores for both the lab data and IMPACT, and determine if the slopes are similar or significantly different (a mixed effect model that will estimate changes in outcomes/slopes). 2) If the slopes are nonlinear, we will calculate the area under the curve (AUC) – a measure of total pain change – up to a CBD/THC ratio of 10 (our high CBD dose in the lab). 3) It is possible that our IMPACT data show that many participants only use one or two types of cannabis (e.g., with only a single CBD/THC ratio), thus it might be difficult to plot a CBD/THC ratio distribution. In that event, we will classify IMPACT cannabis use into 3 categories (low CBD/THC ratio, < 1; matched CBD/THC 1:1; high CBD/THC ratio, >1, and examine the correlation between the pain change in each category (averaged over the IMPACT study) with the pain change scores we observe for our low, medium, and high CBD laboratory doses. If our findings indicate a higher slope or greater AUC for NIDA cannabis vs. dispensary cannabis, this would suggest less efficacious pain relief from the local cannabis sources. In contrast, a strong correlation between CBD pain change scores for NIDA and dispensary product in one or more CBD/THC ratio categories would support a consistent finding for the effectiveness of different CBD amounts. In summary, either agreement or discrepancy between NIDA and dispensary data would be highly informative and would help guide future policy recommendations for cannabis-based pain treatment.

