
time point. All response observations, including information from subjects who do not complete all experimental sessions, will be included in the analyses. Similar mixed-model analyses will be performed on the primary pain outcome after adjustment for psychomimetic side effects (measured with the ARCI scale) to assess for effects of the study drug on pain independent of subjective responses. The proportion of subjects with a 30% pain reduction, a standard for effective pain reduction⁶⁰ will be compared between each of the doses with chi-square tests; we will also calculate the number needed to treat (NNT) for a 30% pain reduction rate. We will also conduct analyses to examine the association between pain and EC biomarkers, including AEA, 2-AG, FAAH, and MAGL expression. A 5% significance level will be used for all testing. The association of pain levels with HRV will use a linear mixed-effects model, adjusting for potential confounders as above. Within-subject correlation will be accounted for using subject-specific random intercepts and slopes.

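### The only stated check that blank IMPACT days are missing completely at random compares people by how much they miss, and has little power against a person skipping replies on particular days

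*Combined protocol and SAP*

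**What the plan says.** Section 7.2 expects some replies to be lost: "we anticipate that participants will respond to 80-90% of the daily text messages during IMPACT". It offers recall as a partial remedy when an earlier message went unanswered: "we will incorporate questions that allow participants to indicate their pain and cannabis use for the prior day". Dropout is kept apart: "Study dropout will be examined separately using statistical methods in current use".

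For days that stay entirely blank, the plan says "we will treat the intermittently missing data as missing completely at random". The check of that takes one sentence: "this assumption will be checked in sensitivity analyses by comparing the outcomes of participants based on the amount of missing data". The section does not say which outcome is compared, how participants are grouped, which test is used, or what result would count against the assumption. It does not describe the recalled reports as a check, and it plans no missing-not-at-random analysis for these gaps.

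The main Aim 2 analysis is a mixed-effects linear model. It relates the pain change around each cannabis event to that event's CBD, THC and CBD/THC ratio: "Subject-specific random intercepts will be included in the model in order to account for the within-subject correlation of the outcome". Section 7.1 sets the level: "A 5% significance level will be used for all testing"; sidedness is not stated.

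**The concern.** The assumption and its check have different units. The assumption is that whether a given day is blank has nothing to do with that day's pain, use or response. The check asks whether a person's outcomes are related to how much that person misses. The second can look clean while the first is false: if everyone skips on their own worse days, frequent and infrequent repliers can still have similar averages.

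The Aim 2 slope draws largely on differences between events in the same person, so selective skipping by day is the kind that can distort it. The SAP could then report the assumption as checked with nearly the same probability whether or not such skipping occurs. Section 7.2 goes on to compare these IMPACT slopes with the laboratory results and ties that comparison to policy advice, so a false reassurance would carry forward.

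**Working it through.** **1. The plan's own figure.** The documents give no power or pass rate for the missingness check. The nearest stated figure is the Aim 2 power in Section 7.4: 80% for R = 0.218.
- Effective sample size: 80 / (0.5 + 0.5/52) = 157; the plan's approximation is 80/0.5 = 160.
- f² = 0.0475/0.9525 = 0.0499, so the noncentrality at 160 is 160 × 0.0499 = 8.0.
- Power is 80.2% at 160 and 79.4% at 157. The figure reproduces.

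**2. Inputs.** From the documents: 80 participants, 52 events each (or 26 × 7 = 182 days), intra-class correlation (ICC) 0.5, 80–90% response, 5% level. Assumed: a two-sided test; logistic non-reply; the odds ratios; the spread of reply rates between people; the autocorrelation of the outcome; and the form of the check (a median-split t test, or a correlation, of each person's observed mean against the fraction missing).

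**3. Pass rate of the planned check.** Outcome = √ICC × person effect + √(1 − ICC) × within-person deviation. The logit of non-reply is a person intercept plus β × within-person deviation. With 15% missing, 52 events, and odds ratios of 1.6, 2.7 and 7.4 per within-person SD (500 runs per cell, Monte Carlo error about 1 point):

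| Reply-rate SD (logit) | Median split passes | Correlation passes |
|---|---|---|
| 0 | 94–95% | 94–97% |
| 0.5 | 93–97% | 95–96% |
| 0.7 | 94–95% | 94–96% |
| 1 | 92–95% | 89–93% |
| 1.5 | 87–93% | 82–90% |

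With 182 days and 10–20% missing included, the lower end is about 85% at SD 1 and 80% at SD 1.5. At ICC 0.2–0.3 with varied reply rates, the check passes 48–86%. When the assumption is true it passes 94–96%.

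If skipping follows the person's overall level as well as the event (SD 0.7), the picture changes. At odds ratios of 1.3, 1.6 and 2.7 the median split passes 47%, 3% and 0%, and the correlation 32%, 0.5% and 0%.

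**4. A within-person check for comparison.** This relates non-reply to the same person's previous answered outcome.
- Daily pain, odds doubling per within-person SD, 85% response: it rejects in about 100% of trials at autocorrelation 0.3 and 62–64% at 0.1, with 4% false alarms. The planned check rejects in 6–9%.
- Event outcomes, odds ratio 2.7: 98–100% at autocorrelation 0.3, 35% at 0.1, 5% at zero.

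**5. Consequence for the dose slope.** 80 × 52 = 4,160 events, true slope zero. Missing odds double per SD of dose and per SD of same-event relief, and nothing is recovered. Ranges span separate simulation runs. The implied slope is (1.96 + z of the rejection rate) × SE, with SE = 1/√(answered events).

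| Response | Answered events | False rejection | Implied spurious slope |
|---|---|---|---|
| 90% | 3,744 | 45–49% | at 45%: 1.83 × 0.0163 = 0.030 |
| 85% | 3,536 | 70% | 2.48 × 0.0168 = 0.042 |
| 80% | 3,328 | 82–84% | at 84%: 2.95 × 0.0173 = 0.051 |

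Slopes are in SD of relief per SD of dose. The planned check fires in only 5–7% of these trials. Other settings:
- Odds ratios of 1.5 at 85% response: 17–21% false rejection.
- Odds ratios of 2 at 85% response, with prior-day recall recovering half the missed events at random (assumed): 17–19%.
- Missingness dependent on relief alone: no false dose effect. A true slope of 0.218 shrinks by about 4% at an odds ratio of 2 and 9% at 3.

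**The case against.** Several objections have force.

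- **Form of the check.** The plan does not say that the outcome compared is mean pain. Comparing dose-response slopes between heavier and lighter non-repliers would also fit the wording and sit closer to Aim 2. A rough calculation suggests little gain. With 40 people at 90% response (1,872 events, slope 0.030) and 40 at 80% (1,664 events, slope 0.051), the difference is 0.021 with SE √(1/1,872 + 1/1,664) = 0.034, so z is about 0.6. A wider spread of reply rates would help.
- **Mitigation.** Recall comes before the assumption is applied, so unanswered messages are not all lost events. The plan gives no recovery rate, and it is unclear whether recall returns full before-and-after scores.
- **Size.** A spurious slope of 0.03–0.05 SD is small beside the plan's 0.218. It becomes significant because there are several thousand events. It also assumes that dose varies freely within person, while Section 7.2 allows that many participants may use only one or two products. Nothing in the documents supports or excludes the assumed odds ratios.
- **Model.** A likelihood-based mixed model needs only missing at random, so part of the protection is already implied.
- **Limits of any check.** In the dose-and-relief scenario, a check on the previous event's relief detects the problem in 92% of trials at autocorrelation 0.3, 21% at 0.1 and 5% at zero.

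These limit the size of the harm and the claims that can be made for a remedy. They do not give the planned comparison power against skipping by day.

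**Conclusion.** The point holds in a limited form. The stated check has little power against purely within-person skipping: at ICC 0.5 and reply-rate SD up to 1, it passes a false assumption in roughly 85–97% of trials, close to its pass rate when the assumption is true. The consequence for Aim 2 runs from slight attenuation to frequent but small false dose effects, depending on a mechanism and a recall rate that the documents do not give.

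A reader might infer more than this, and the documents do not support it:
- That the check fails at one fixed rate, or sees nothing. It has good power when skipping follows overall pain level, and some when reply rates vary widely.
- That it errs by rejecting when people in more pain reply less. Such data are not missing completely at random, so the rejection is correct, even if a within-person slope is unharmed.
- That a 70% false-positive rate is to be expected. That figure needs strong dependence on both dose and relief and no recovery by recall.

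The section should be amended before analysis. The point does not invalidate Aim 2.

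**What to change.** Keep the between-participant comparison as descriptive, and add to Section 7.2:

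1. A within-participant check: a mixed or conditional logistic model of non-reply on the same person's last answered pain and last reported use, centred on that person's mean. Alongside it, compare recalled prior-day pain and use with the same person's answered days.
2. A statement that the Aim 2 mixed model is likelihood-based and relies on missing at random, not on missing completely at random.
3. One missing-not-at-random sensitivity analysis that shifts unobserved pain changes by a stated amount, allowed to differ by dose, and reports the shift at which the CBD/THC conclusion changes. Use is also unobserved on a blank day, so the SAP should say how it is filled in for this analysis.

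The cost is SAP wording and programming on data already collected, with no new visits or procedures. The lagged check in item 1 loses power as day-to-day autocorrelation nears zero. No check on observed data can exclude missingness that depends on the unobserved response, which is why item 3 is needed as well.

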For Aim 2, with 20% attrition over the 6 months of IMPACT we have $n= 80$ participants with 6 months (26 weeks) of data. We conservatively ignore the drop-out participants (who nonetheless contribute partial data). Assume, conservatively, that participants will use cannabis on average 2 times/week. This gives $n=80$ and $k=52$ observations/participant. If ICC is the intra-class, or within-participant correlation, the effective sample size (number of equivalent independent observations) is $n_{\text{eff}} = n/(ICC+(1-ICC)/k) \approx n/ICC$ [e.g., Killip, Mahfoud, Pearce, Ann Fam Med, 2004; 2:204-208.]. Assuming conservatively $\rho=0.5$ (or lower), we get $n_{\text{eff}} = 2n = 200$ [$n_{\text{eff}} = 160$]. We have 80% power to detect a (partial) correlation R between the individual predictors (Hypothesis 1: CBD, THC, and the CBD/THC ratio; Hypothesis 2: pain levels and HRV) and change in pain of $R = 0.218$ (or semi-partial $R^2 = 0.0475$), after adjusting for confounders. Calculations used G*Power.

For Aim 3, assuming $n = 80$ participants complete the 6-month follow-up, we have 80% power to detect an association between an individual predictor and response (e.g., total CBD and changes in neuropathic pain levels) of $R = 0.302$ (or semi-partial $R^2 = 0.092$), after adjusting for confounders. The calculations used G*Power.

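### The Aim 2 event-level model does not separate within-person from between-person effects of CBD, THC and their ratio, so its slope is a mix of the two

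*Combined protocol and SAP*

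**What the plan says.** Section 7.2 defines the Aim 2 question at the level of the event: "The relationship between CBD, THC, and the CBD/THC ratio during a cannabis exposure event to changes in pain before and after the event". The analysis "will be examined using longitudinal data methods – e.g., mixed-effects linear models, controlling for potential confounders including baseline pain", together with the covariates listed for Aim 1 in section 7.1. The only structural statement about this model is "Subject-specific random intercepts will be included in the model in order to account for the within-subject correlation of the outcome".

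Nothing in the documents describes person-mean centring, fixed participant effects or any other within/between split. Random slopes appear only for the Aim 1 model of pain and HRV in section 7.1: "Within-subject correlation will be accounted for using subject-specific random intercepts and slopes".

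Three other statements bear on the point:

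- Section 7.2, in the comparison of NIDA and dispensary cannabis, allows that it is possible that "many participants only use one or two types of cannabis", and gives a single CBD/THC ratio as the example.
- The same comparison sets the IMPACT slope of pain change on the ratio against the laboratory slope.
- Section 7.4 takes 20% attrition and an average of two uses a week: "This gives $n=80$ and $k=52$ observations/participant". It assumes an outcome intraclass correlation of 0.5 or lower.

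**The concern.** In IMPACT, participants choose the product and the amount. Two comparisons then sit in the data: a person's higher-CBD events against the same person's lower-CBD events, and people who generally use high-CBD products against people who do not. The second can reflect why people choose what they choose. Repeated events are valuable because the first comparison lets each person act as his or her own control.

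A mixed model with a raw event-level exposure and a random intercept assumes that the two slopes are equal and averages them by precision. If they differ, the reported slope is neither one.

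The matter carries into the comparison with the laboratory crossover. There every participant is to receive all three doses, so the ratio varies within person by design. The plan would read a steeper laboratory slope as less effective pain relief from local products. A between-person component in the IMPACT slope could create or hide such a difference.

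**Working it through.** **Inputs.** From section 7.4: n = 80, k = 52 events per person, outcome intraclass correlation ρ = 0.5 or lower. From the Schema: light use is 1–4 times a month, so 6–24 events in six months. From section 7.1: a 5% significance level (two-sided assumed). Not in the documents: the share r of exposure variance that lies between people, so a range is shown.

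**1. The plan's own figure.** Effective size = n/(ρ + (1−ρ)/k) = 80/(0.5 + 0.5/52) = 157.0, or 80/0.5 = 160 by the plan's approximation. The F test of one coefficient at N = 160 has 80% power at R = 0.2175, and 80.2% power at the stated R = 0.218. The figure reproduces. The formula is the one for a predictor that is constant within a person.

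**2. Weight of the between-person slope.** For a balanced random-intercept fit:

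- ψ = (1−ρ)/(1−ρ+kρ)
- B = ψ(kr + 1 − r)
- W = (k−1)(1−r)
- weight = B/(B+W)

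At k = 52 and ρ = 0.5, ψ = 0.5/26.5 = 0.01887. For r = 0.80, B = 0.01887 × 41.8 = 0.789, W = 51 × 0.2 = 10.2, and the weight is 0.789/10.989 = 7.2%.

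| Between-person share r | k=52, ρ=0.5 | k=52, ρ=0.1 | k=12, ρ=0.5 | k=6, ρ=0.5 |
|---|---|---|---|---|
| 0.50 | 1.9% | 13.3% | 8.3% | 16.7% |
| 0.80 | 7.2% | 37.7% | 25.5% | 41.7% |
| 0.90 | 14.8% | 57.6% | 43.3% | 61.1% |
| 0.95 | 26.8% | 74.1% | 61.6% | 76.7% |
| 0.99 | 65.6% | 93.7% | 89.3% | 94.4% |

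The last two columns apply only if every participant has that few events. With half light and half heavy users averaging 52 events (12/92, 6/98 or 24/80), the weight at ρ = 0.5 stays at 7% for r = 0.80 and 26–27% for r = 0.95. Within-person information grows with k−1, so the heavy users supply most of it.

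**3. Simulation.** The true within-person slope was 0 and the assumed between-person slope −0.5, with n = 80 and 60 runs per setting, so rejection rates are approximate.

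| r, k, ρ | Mean slope, unsplit model | Rejections at 5% | Mean within slope, split model |
|---|---|---|---|
| 0.50, 52, 0.5 | −0.008 | 8% | −0.001 |
| 0.90, 52, 0.5 | −0.056 | 38% | 0.001 |
| 0.95, 52, 0.5 | −0.105 | 68% | 0.000 |
| 0.90, 12, 0.5 | −0.195 | 88% | −0.005 |
| 0.90, 52, 0.1 | −0.242 | 100% | −0.009 |

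The unsplit slopes are slightly smaller than weight × (−0.5), because the unmodelled between-person difference enlarges the estimated participant variance and so lowers the between-person weight.

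**4. Precision after a split.** The effective size for the within-person slope, on the total-variance scale, is n(k−1)(1−r)/(1−ρ) = 80 × 51 × (1−r)/0.5 = 8160(1−r). The detectable R at 80% power is 0.044 at r = 0.50 (4080), 0.098 at 0.90 (816), 0.138 at 0.95 (408), 0.215 at 0.98 (163) and 0.300 at 0.99 (82). The stated 0.218 is met until r reaches about 0.98.

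**The case against.** The strongest reply is about size. At the plan's own k and ρ, with half the exposure variance between people, the between-person weight is 2%. That stands, and no figure in the documents shows that the share is high.

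Several stronger readings are tempting, and the documents do not support them:

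- *The slope would take the wrong sign.* Assume a within-person slope of −0.30 and a between-person slope of +0.30. At r = 0.95 and k = 52 the mix is −0.30 + 0.60 × 0.268 = −0.14, attenuated but of the right sign. At 12 events for everyone it is −0.30 + 0.60 × 0.616 = +0.07 (about +0.05 in simulation). The reversal needs a cohort with few events throughout, and neither slope comes from the documents.
- *Light users drive the result.* In a mixed cohort averaging 52 events they barely change the weight.
- *Differences between people are uncontrolled.* The plan adjusts for baseline pain and for the Aim 1 list, which includes light or heavy use, lifetime duration of use, time since last use and other analgesics. The outcome is a change score, which partly removes stable differences in pain level. What remains is residual confounding. It is a fair worry, because section 7.1 screens that list at α = 0.20 and measured covariates cannot cover every reason for choosing a product.
- *The plan expects single-product use.* It says only that this is possible. The argument also fits the ratio best: CBD and THC are grams consumed times percentage content, so they vary with amount even for one product.
- *The plan rules out a split.* The mixed model is given as an example, and a split would contradict nothing. The within-person target is a reasonable reading of an event-level question, not a stated one. That openness also leaves the estimate undefined until the data are seen.

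**Conclusion.** The point holds as a gap in what the Aim 2 slope estimates. Fitted as described, with raw event-level exposures and random intercepts only, the model yields a precision-weighted mix, and no section separates its parts. At k = 52 and ρ = 0.5 the between-person weight runs from about 2% to 27% for a between-person exposure share of 50% to 95%, and reaches 66% at 99%. It is larger if ρ is below 0.5, which section 7.4 allows (58% at ρ = 0.1 with a 90% share), or if events per person are generally few.

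These weights rest on the assumed share, on a balanced random-intercept fit, and on ρ being the correlation left after the covariates. The weight becomes bias only so far as the between-person slope still differs from the within-person slope after adjustment, and the documents cannot show whether it does. The CBD/THC ratio is the exposure most at risk, and with it the comparison against the laboratory slope. The stated power figure is not in dispute.

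**What to change.** In section 7.2:

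1. Enter each of CBD, THC and the CBD/THC ratio as two terms: the participant's mean over IMPACT events and the event's deviation from that mean.
2. Name the within-person coefficient as the Aim 2 estimate, and use the within-person ratio slope as the IMPACT slope in the comparison with the laboratory data.
3. Report the between-person coefficient separately, as associational.
4. State whether baseline pain means pain just before the event, and make adjustment for pre-event pain explicit. The split does not remove event-level confounding, such as taking more on worse-pain days, and the plan should state that limit.

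The cost is one extra term per exposure and a few sentences, with no new data or participants. The within-person interval will be wider, and participants with a single ratio contribute nothing to the within-person ratio slope. The stated R = 0.218 remains within reach unless about 98% or more of the exposure variance lies between people. In that case the data hold little within-person evidence, and the report should say so.

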HIV-associated neuropathic pain (HIV-NP) affects a significant proportion of people living with HIV (PLWH) and has a major impact on everyday functioning and quality of life in this population. Over the past decade a growing number of preclinical studies and clinical trials have indicated that cannabis administration and manipulation of the endocannabinoid (EC) system may have therapeutic utility in addressing HIV-NP. EC CB2 receptor activation and inhibition of the EC deactivation enzymes fatty acid amide hydrolase (FAAH) and monoacylglycerol lipase (MAGL) have been shown to decrease pain in rodent models of HIV-NP, while acute exposure to cannabis reduces self-reported pain in PLWH with neuropathy. However, little work has been conducted to elucidate the effects of the two primary cannabinoids (delta-9-tetrahydrocannabinol, THC and cannabidiol, CBD) on the EC system or to assess EC function in PLWH. The objective of this application is to address these fundamental gaps in our knowledge by: 1) examining the acute effect of administering NIDA-prepared THC/CBD products on HIV-NP; 2) utilizing mHealth text messaging to monitor daily real-world self-administered cannabis effects on pain; 3) assessing the relationship between cannabinoids and EC biomarkers, including ligands, enzymes, and receptor expression; and 4) conducting exploratory analyses to evaluate the effect of longitudinal cannabinoid use on changes in HIV-NP over time. We will examine the effect of low (0.01%), medium (one vial of 5.1%), and high dose (two vials of 5.1%) CBD-containing cannabis on NP, the EC system, and heart rate variability (as a proposed objective biological measure of pain) in 100 PLWH who use cannabis to treat neuropathic pain. We will subsequently employ a mobile phone text messaging system, the Individual Monitoring of Pain And Cannabis Taken (IMPACT), to track cannabis exposure, CBD and THC consumption, and pain over a period of 6 months in these same PLWH participants. IMPACT will be used to quantify the real-time effects of acute CBD/THC exposure on pain before and after cannabis self-administration, the real-time relationship between self-reported pain and changes in HRV, and to assess any longitudinal changes in NP, HIV clinical outcomes (viral load, CD4) and cognition during the 6-month period. This plan allows us to acquire data and compare the effects of cannabis product obtained from NIDA and self-administered cannabis obtained from local medicinal dispensaries. The overarching hypothesis is that CBD exposure and a higher CBD/THC ratio will exert beneficial effects both in the laboratory and during the observational study, including increasing EC biomarkers and reducing NP. In summary, this approach will advance our understanding about several key issues, including the interaction between cannabis constituents, the EC system and pain, the biological mechanisms that underlie these effects (EC enzymes, receptor), and the longer-term effects of cannabis use on health-related outcomes in HIV, including predictors of mortality (HRV, CD4, viral load) and neurocognition.

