7.3 Aim 3 Measures and Analyses

We will use a linear model to examine the association between the total CBD, THC, and CBD/THC ratio during IMPACT and the change in NP, disease markers (CD4, viral load, Total Neuropathy Score, and neurocognitive global T-score), and EC biomarkers (AEA, 2-AG, FAAH, MAGL, CB2) from baseline to the final visit after month 6. We will control for confounders as in Aims 1 and 2, including any CBD and THC levels recorded at the baseline and final sessions. Linear models will compare the month 6 – baseline change in pain and in EC biomarkers between the heavy- and light-cannabis groups. One exploratory analysis will test for an interaction between group (light vs. heavy) and CBD and THC levels on change in NP and EC biomarkers. We will assess if exposure mode (smoking/vaporizing/ingestion) predicts pain outcome. We will examine if there is an association between pain change over time and changes in EC biomarkers. During the 6-month IMPACT, alterations may occur in cannabis use or pain medication (e.g., a person enrolled as a light cannabis user may start to engage in heavy use or begin using non-cannabis medication for pain, i.e., an opiate, which we will record with IMPACT). To address these issues we will conduct light vs. heavy use analyses based both on the baseline group classification and the actual use during IMPACT, include a cannabis use 'change' factor in the analyses (going from light to heavy use, or vice versa), and include the initiation of any non-cannabis pain medication as a factor in the model.

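### The Aim 2 daily pain-HRV model names no study-time term, so a slow trend in both series over 26 weeks would be mixed into their real-time association

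*Combined protocol and SAP*

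**What the plan says.** Section 7.2 describes two repeated-measures models for IMPACT.

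- **Daily model.** "The association of daily measures of pain levels with HRV will use a linear mixed-effects model, adjusting for potential confounders". The confounders are not listed. On correlation it adds: "The within-subject correlation will be accounted for using subject-specific random intercepts".
- **Event model.** The outcome is a change score: "The relationship between CBD, THC, and the CBD/THC ratio during a cannabis exposure event to changes in pain before and after the event". The method is given as "mixed-effects linear models, controlling for potential confounders including baseline pain, in addition to those listed under Aim 1", again with random intercepts: "Subject-specific random intercepts will be included in the model in order to account for the within-subject correlation of the outcome".

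The Aim 1 list in section 7.1 holds histories of use, disease factors, gender and medication. Its timing items are the time since last use before baseline and durations of use or infection. The time and time-squared terms in 7.1 are minutes after a laboratory dose. Calendar position within IMPACT appears in neither section as a covariate.

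The plan treats slow change as a separate question. The opening summary lists "the real-time relationship between self-reported pain and changes in HRV, and to assess any longitudinal changes in NP" as distinct purposes. Section 7.2 has its own analysis for slow HRV change: "Longitudinal changes in HRV between the first and last week will be assessed with a linear model". Section 7.3 notes: "During the 6-month IMPACT, alterations may occur in cannabis use or pain medication". It answers with a use-change factor and a factor for starting pain medication, but only in the Aim 3 models.

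**The concern.** A random intercept removes stable differences between people. It does not remove a trend within people. If pain ratings and HRV both move over six months for reasons unrelated to each other (reporting habituation, for example), early days differ from late days on both variables. A model without study time reads that as same-day association. Random slopes on HRV or person-mean centring would not help when the trend is common to participants, because it lies within each person's own series.

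The coefficient at stake answers the second Aim 2 hypothesis in section 7.4 (pain levels and HRV). It would blend the real-time relation with the slow change that the plan intends to examine elsewhere.

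**Working it through.** **1. The plan's own figure.** Inputs from section 7.4: n = 80, k = 52 events, ICC = 0.5, 26 weeks. Section 7.1 gives the 5% level; two-sided testing is assumed.

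n_eff ≈ n/ICC = 80/0.5 = 160 (exact: 80/(0.5 + 0.5/52) = 157). With R = 0.218, R² = 0.0475 and f² = 0.0475/0.9525 = 0.0499, the noncentrality is √(0.0499 × 160) = 2.82 and power is 0.802. The stated R reproduces at n_eff = 160. (The 200 printed beside it belongs to n = 100 and would give R = 0.195.) This calculation contains no time term. It supplies inputs and a yardstick.

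**2. Size of the artefact, daily model.** Assumptions, none of them in the documents: a linear drift of d within-person SD over 26 weeks in both series, common to participants; independent within-person errors; HRV available on every day with a text response. Readings per person: 182 days × 0.85 (the middle of the 80-90% response in 7.2) ≈ 155. Total N = 80 × 155 = 12,400, and √N ≈ 111.4.

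A linear trend of total size d has variance d²/12. With unit within-person variance, the spurious within-person correlation is about d²/12, and z ≈ (d²/12) × √N.

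| d | d²/12 | z | False positives, simulated | With linear study time |
|---|---|---|---|---|
| 0.2 | 0.0033 | 0.37 | 7% | 4-6% |
| 0.3 | 0.0075 | 0.84 | 14% | 4-6% |
| 0.4 | 0.0133 | 1.49 | 30% | 4-6% |
| 0.5 | 0.0208 | 2.32 | 64% | 4-6% |

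The simulation had no true association, n = 80, ICC 0.5 and 2,000 replicates per row. The formula agrees: at d = 0.5, P(Z > 1.96 − 2.32) = 0.64. If drifts run in opposite directions, the sign reverses and the size is the same. If the within-person SD of the pain rating is 1.5 points (assumption), 0.3 to 0.5 SD is 0.45 to 0.75 points on the 0-10 scale over six months.

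A correlation of 0.02 can be significant although the planned detectable R is 0.218 because the slope is estimated mainly from within-person variation across 12,400 readings. The plan's effective sample size is 160.

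**3. A second simulation in other units.** Drift was expressed in total SD, with 182 readings and 400 runs per cell. At ICC 0.5 one within-person SD is √0.5 = 0.71 total SD, so 0.3 total SD is 0.3/0.71 = 0.42 within-person SD. False positives were 46% at 0.3 total SD and 99.5% at 0.5, falling to 5% and 3% with a linear time term. Allowing for units and reading count, this agrees with the table.

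**4. The event model.** The outcome is post minus pre. A drift in pain level enters both ratings and cancels. With 1 SD of level drift and drifting intake, simulation gave 6% false positives and a slope near zero. Only a drift in the response itself, alongside drift in product content, produces the artefact. In that case N = 80 × 52 = 4,160 and √N ≈ 64.5. At d = 0.5, z = 0.0208 × 64.5 = 1.34, which gives 27%. Simulated rates were 8% at 0.3, 14% at 0.4 and 27% at 0.5 SD of the change score.

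**5. Person-specific trends.** A common time term removes only common drift. With individual trends of SD 1.0 added to a common drift of 0.5, the daily model gave a little over half false positives without time, about 16% with a common time term, and about 5% once a participant-specific slope on time was included.

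**The case against.** Several counter-arguments stand.

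- The confounder wording is open in both models. Study time is unspecified, not excluded, and an analyst could add it.
- The documents give no size or direction for any drift. They plan to look for six-month change, and the use changes in 7.3 may go either way. A reader might infer that the plan expects everyone to drift the same way; the text does not say so.
- At 0.2 SD the inflation is negligible (7%).
- No HRV schedule for IMPACT is given, so 155 readings is an assumption, as is independence of the daily errors. The return to 4-6% is partly built in, because the simulated drift was linear and common.

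A reader might also infer that any shared drift is counted as a CBD/THC effect on pain. That does not follow, because level drift cancels in a change score. Nor can the point borrow weight from the primary outcomes: section 2.0 lists dispensary cannabis and changes in pain for Aim 2, and names HRV only under Aim 1.

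The objection does not remove the gap. Section 7.1 names its time terms and 7.2 names none, so the choice would otherwise be left to the analysis stage.

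**Conclusion.** The point holds for the daily pain-HRV model, as a cheap improvement. No study-time term is specified, and nothing elsewhere supplies one for Aim 2. Under a shared linear drift of 0.3 to 0.5 within-person SD and the other assumptions above, false positives are about 14% to 64% against a nominal 5%. The induced correlation is about 0.008 to 0.02, roughly a tenth of the planned detectable R or less. The risk is therefore a significant but trivial association read as a real-time link.

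It would go too far to say that drift could readily hide or reverse a true effect of the planned size. Cancelling R = 0.218 needs d²/12 = 0.218, that is d = √2.616 ≈ 1.6 within-person SD in each series, in opposing directions.

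For the CBD/THC event model the concern is conditional. It needs drift in the pre-to-post response, such as tolerance or a floor effect as pain falls, together with drift in product content.

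**What to change.** In section 7.2, add study week since the start of IMPACT to the daily pain-HRV model as a fixed effect (linear, with a quadratic or spline term), with a participant-specific random slope on study week. Add the same terms to the CBD/THC event model as a safeguard. State that the HRV and CBD/THC coefficients are effects at a given study time. Leave slow six-month change to the HRV change analysis in 7.2 and the month-6 analyses in 7.3.

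The cost is a sentence or two of text and a few degrees of freedom among thousands of readings. There is one small downside: if pain and HRV truly move together slowly, that part no longer counts towards the daily coefficient. The planned longitudinal analyses still cover it.
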